### **Analysis Timing Projections**

As stated above, approximately 726 subjects will be randomized to the two treatment arms in a 1:1 ratio.

- It will take approximately 13 months to complete the randomization.
- OS interim analysis is projected to occur when there are at least 416 deaths (80% of target events) among approximately 726 randomized subjects, approximately 25 months after the first subject's randomization date (13 months for randomization and 12 months for survival follow-up).
- OS final analysis is projected to occur when there are at least 520 deaths among approximately 726 randomized subjects, approximately 33 months after the first subject's randomization date (13 months for randomization and 20 months for survival follow-up).

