4.1.1 ORR

ORR is defined as the proportion of subjects whose best overall response (BOR) is either a complete response (CR) or partial response (PR) among all randomized subjects in a population of interest. BOR is defined as the best response designation recorded between the date of randomization and the date of first objectively documented progression or the date of subsequent anti-cancer therapy, whichever occurs first. For subjects without documented progression or subsequent anti-cancer therapy, all available response designations will contribute to the BOR determination. For a BOR of CR or PR, the initial response assessment must be confirmed by a consecutive assessment no less than 4 weeks (28 days) later. In the case of stable disease (SD), measurements must have met the SD criteria at least once after randomization at a minimum of 7 weeks (49 days). **Responder** is defined as a subject whose BOR is either a CR or PR.

Tumor imaging assessments will occur 8 weeks from the date of randomization (+/- 1 wk), then every 8 weeks (+/- 1 wk) thereafter up to 48 weeks, then it will be every 12 weeks (+/- 1 week) until disease progression or treatment is discontinued (whichever occurs later).

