Let $i = 1, 2, 3$ denote index indicating primary endpoint OS and secondary endpoints ORR and PFS, respectively. Accordingly, H_1, H_2, H_3 denote two-sided null hypotheses of no effect in primary endpoint OS and secondary endpoints ORR and PFS, respectively. Let $t = 1, 2$ denote

index indicating interim and final analysis timings, respectively. Correspondingly, $p_{i,t}$ denote nominal p-value of testing H_i at the analysis time t , and the corresponding decision boundaries can be expressed as nominal significance levels $a_{i,t}^*$ such that H_i is rejected if $p_{i,t}$ is smaller than $a_{i,t}^*$ at time t .

To strongly control FWER at level 0.05 across three endpoints and repeated analyses at interim and final analyses, we adopted the stagewise hierarchical testing procedure³⁶ to test H_1 , H_2 , H_3 . Specifically, at the interim analysis time H_1 is tested with nominal significance level $a_{1,1}^*$ leading to the following two possibilities of rejecting H_1 :

[figure not shown]
- If $p_{1,1} < a_{1,1}^*$, H_1 will be rejected, the trial will stop and H_2 will be tested with nominal significance level $a_{2,1}^*$. If $p_{2,1} < a_{2,1}^*$, H_2 will be rejected and H_3 will be tested with nominal significance level $a_{3,1}^*$ with $p_{3,1} < a_{3,1}^*$ leading to the rejection of H_3 . If $p_{2,1} \geq a_{2,1}^*$, H_2 will not be rejected and H_3 will not be tested.
- If $p_{1,1} \geq a_{1,1}^*$, the trial continues to final analysis time and H_1 will be tested with nominal significance level $a_{1,2}^*$. If $p_{1,2} < a_{1,2}^*$, H_1 will be rejected and H_2 will be tested with nominal significance level $a_{2,2}^*$. If $p_{2,2} < a_{2,2}^*$, H_2 will be rejected and H_3 will be tested with nominal significance level $a_{3,2}^*$ with $p_{3,2} < a_{3,2}^*$ leading to the rejection of H_3 . If $p_{2,2} \geq a_{2,2}^*$, H_2 will not be rejected and H_3 will not be tested.

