The nominal significance levels for OS $a_{1,1}^*$ and $a_{1,2}^*$ will be computed using EAST software based on a generalization of the Lan-DeMets error spending function approach using an O'Brien-Fleming stopping boundary given overall two-sided alpha = 0.05. The stopping boundary will depend on the actual number of OS events observed at the time of the interim analysis and the final analysis. However, if the interim analysis is performed exactly when 80% OS events are observed, then $a_{1,1}^* = 0.024$ will be used for the interim analysis and $a_{1,2}^* = 0.043$ will be used for the final analysis.

The nominal significance levels for ORR will be pre-specified as $a_{2,1}^* = 0.025$ and $a_{2,2}^* = 0.025$, as an equal Bonferroni splitting of the two-sided alpha = 0.05.

The nominal significance levels for PFS $a_{3,1}^*$ and $a_{3,2}^*$ will be computed using EAST software based on a generalization of the Lan-DeMets error spending function approach using an Pocock stopping boundary given overall two-sided alpha = 0.05. The stopping boundary will depend on the actual number of PFS events observed at the time of the interim analysis and the final analysis. 722 PFS events are expected at the final analysis time (of OS). 704 out of 722 or 97.5% PFS events are expected at the interim analysis time. If the interim analysis is performed exactly when 97.5% PFS events are observed, then $a_{3,1}^* = 0.049$ and $a_{3,2}^* = 0.031$ will be used.

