7.10 Post Hoc Analyses

This section documents the statistical analyses plan being or to be conducted after the primary database lock for final OS analyses (Database locked on June 05, 2019). For ease of reference in this section, vascular invasion will be referred to as VI; extrahepatic spread will be referred to as EHS; correspondingly, vascular invasion and/or extrahepatic spread will be referred to as VI/EHS.

There are three types of analyses.

- Section 7.10.1 documents planned analyses using the VI/EHS stratification factor determined by BICR (see Independent Radiology Review Charter³²) and efficacy data from the same database lock indicated above. BICR review of baseline scans is planned to be completed and BICR-based VI/EHS stratification factor locked in approximately August 2020. Analysis results will be summarized in a clinical study report (CSR) addendum.
- [Section 7.10.2](#) documents post-hoc sensitivity analyses for the primary endpoint of OS using statistical methods which account for the non-proportionality of the observed OS curves.

Results of all above analyses will be summarized in clinical summary documents to support regulatory filings.

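### Does the 0.025/0.025 split for ORR waste alpha that a single test at 0.05 should have used?

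*SAP*

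**What the plan says.** SAP 7.5.4.2 sets a familywise error of 0.05 over OS, ORR and PFS and over two analysis times. ORR receives 0.025 at the interim and 0.025 at the final, "as an equal Bonferroni splitting of the two-sided alpha = 0.05". If OS succeeds at the interim, "H_1 will be rejected, the trial will stop and H_2 will be tested with nominal significance level" 0.025. If OS succeeds only at the final, ORR is tested there, also at 0.025. On any path ORR is therefore tested at most once. PFS in the same section uses Pocock-type spending, because "704 out of 722 or 97.5% PFS events are expected at the interim analysis time", which gives 0.049 and 0.031.

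On maturity, SAP 4.1.1 closes the response window early: "BOR is defined as the best response designation recorded between the date of randomization and the date of first objectively documented progression", or at subsequent therapy if that comes first. Scans run at week 8, "then every 8 weeks (+/- 1 wk) thereafter up to 48 weeks", and every 12 weeks after that. A response counts only if confirmed: "the initial response assessment must be confirmed by a consecutive assessment no less than 4 weeks (28 days) later". Protocol 8.1 places the OS interim at about month 25 ("13 months for randomization and 12 months for survival follow-up") and the final at about month 33.

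**The concern.** Bonferroni takes no credit for overlap between the two possible ORR datasets, and here the overlap should be large. At the interim the last subject has about 12 months of follow-up, and on the SAP's projection only 726 − 704 = 22 subjects have no PFS event. PFS is given credit for such overlap; ORR is not, and the SAP does not say why. ORR is also the only gate to PFS, so a needlessly strict level would lower the chance of a confirmatory ORR result and of reaching the PFS test. An alternative exists: freeze the ORR data at the OS-interim cutoff and test once at 0.05 when OS is first rejected.

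**Working it through.** **1. The plan's own figures.** By the union bound, P(false ORR rejection) ≤ 0.025 + 0.025 = 0.05, whatever the dependence between looks or between endpoints. The neighbouring levels also reproduce. Lan-DeMets O'Brien-Fleming at 416/520 gives 0.0244 and 0.0429 (stated 0.024, 0.043). Pocock-type spending at 704/722 = 0.975 gives 0.0492 and 0.0307 (stated 0.049, 0.031).

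**2. How much error the split uses.** Let f be the share of final responses already seen at the interim, p2 the final ORR and p1 = f·p2. The interim-final correlation is r = √[p1(1−p2)/(p2(1−p1))]. The chance of crossing at either look is 1 − P(|Z1| ≤ 2.241, |Z2| ≤ 2.241). For f = 0.95 and p2 = 0.10, r = √(0.095×0.90/(0.10×0.905)) = 0.972 and the result is 0.031. For f = 0.80, 0.90 and 0.98 it is about 0.037, 0.034 and 0.029.

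That is the error of a rule that looks twice; the SAP looks once, behind OS. I simulated the gated rule at OS HR 0.74 with r from 0.90 to 0.98 and OS-ORR correlation from 0 to 0.5. It gives 0.019 to 0.023. Over wider OS effects and correlations it stays near 0.025. The largest simulated value (one-sided, doubled) is 0.031, at OS-ORR correlation 0.95 and r = 0.88. So the split is conservative, and more so than the two-look figure suggests.

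**3. What a single test at 0.05 would gain.** The documents give no ORR rates, so these are assumptions. Exact power, 363 per arm, same data at both levels:

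| nivolumab vs sorafenib | at 0.025 | at 0.05 |
|---|---|---|
| 10% vs 7% | 0.210 | 0.304 |
| 12% vs 7% | 0.522 | 0.638 |
| 10% vs 5% | 0.630 | 0.731 |
| 14% vs 7% | 0.805 | 0.877 |
| 15% vs 7% | 0.893 | 0.939 |
| 15% vs 5% | 0.992 | 0.996 |

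**4. Where it would lose.** If OS is rejected only at the final, the plan tests newer data at 0.025, while the alternative tests interim data at 0.05. Let k be the net responders nivolumab gains after the interim:

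| rates at interim | plan, k=0 | plan, k=2 | plan, k=3 | plan, k=5 | alternative |
|---|---|---|---|---|---|
| 12% vs 7% | 0.522 | 0.612 | 0.655 | 0.735 | 0.638 |
| 14% vs 7% | 0.805 | 0.860 | 0.884 | 0.922 | 0.877 |

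The plan is ahead from k = 3. On the same path, the usual two-proportion formula with both arms scaled by f gives, for final rates of 10% vs 5%, 0.625 for the plan against 0.702, 0.677 and 0.622 at f = 0.95, 0.90 and 0.80. For 15% vs 7% it gives 0.887 against 0.919, 0.903 and 0.862. The gain has gone at 80% maturity.

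**5. Averaging over the two looks.** The OS drift is ln(1/0.74)·√d/2, which is 3.071 at d = 416 and 3.433 at d = 520. With levels 0.024 and 0.043, OS is rejected at the interim with probability 0.792 and overall with 0.925, so 0.792/0.925 = 0.856 of rejections fall at the interim. With ORR independent of the OS path, the net change for k = 0 to 22 is +11.6 to +4.8 points at 12% vs 7%, and +4.6 to +3.0 at 15% vs 7%. If only half of the OS rejections fall at the interim, as a delayed effect could produce, the alternative turns negative at k = 6 to 9, depending on the rates.

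**6. How firm the maturity is.** With the accrual in SAP Table 5-1 and a single exponential without censoring, 704 events at month 25 and 722 at month 33 both require a PFS median of about 3.2 months. Assumed medians of 4, 5 and 6 months leave about 44, 75 and 108 subjects without an event at month 25. Some of those response windows would be closed by subsequent therapy. Confirmation matters too: the 82 subjects randomized in month 13 have 52 to 56.5 weeks of follow-up at month 25 (13 × 30.4375/7 = 56.5), short of the scheduled week-60 scan. A response first seen at week 48 could still await its scheduled confirmation.

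**The case for a change.** The strongest case for the concern is that its arithmetic is right. Part of the alpha goes unused. The frozen-data test is valid whatever the correlation between OS and ORR: there is one test on one dataset, and its simulated error did not exceed 0.05 beyond simulation noise. Under the design's constant HR and high maturity it raises power on average. All of that stands.

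The contrast with PFS is weaker than it looks. PFS has an event count to serve as its information fraction; best overall response has none. Spending on the share of subjects with a PFS event (704/726) would give 0.0490 and 0.0298, and the two-look error of those levels is 0.051 to 0.053 with 4 expected late responders and 0.059 to 0.063 with 22. A fixed split avoids that risk without any assumption. Its reason could have been stated in a sentence, but leaving it out makes nothing wrong.

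The alternative also costs more than a wording change. It needs central-review responses cleaned and locked at the interim cutoff even when OS continues, and SAP 7.5.4.1 describes no such lock. ORR had been demoted from co-primary in August 2017 in an open-label trial. Relaxing its level at the next SAP version (November 2017) would have invited the question of what was already known about response.

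**Conclusion.** The concern does not hold. The ORR levels are prespecified, sum to 0.05, and protect the familywise error under any dependence, which is the aim SAP 7.5.4.2 sets. They are conservative, with an ORR error of about 0.02 at the design hazard ratio. The alternative is equally valid and sometimes more powerful: by up to about 12 points at mid-range power, by almost nothing for a large ORR difference, and by a negative amount if OS crosses only at the final and at least three net late nivolumab responses arrive.

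Which rule is better turns on ORR rates the documents do not give, on maturity inferred from a projection that fits only a PFS median near 3.2 months, and on a constant OS hazard ratio. Statisticians could reasonably choose either. The OS conclusion is unaffected. The current SAP describes work done "after the primary database lock for final OS analyses (Database locked on June 05, 2019"), so the levels could not properly be changed for this trial in any case.

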7.6 Safety

7.6.1 Deaths

See Core Safety SAP.³³

7.6.2 Serious Adverse Events

See Core Safety SAP.³³

7.6.3 Adverse Events Leading to Discontinuation of Study Therapy

See Core Safety SAP.³³

7.6.4 Adverse Events Leading to Dose Modification

See Core Safety SAP.³³

7.6.5 Adverse Events

See Core Safety SAP.³³

7.6.6 Select Adverse Events

See Core Safety SAP.³³

7.6.7 Immune modulating medication

See Core Safety SAP.³³

7.6.8 Multiple Events

See Core Safety SAP.³³

7.6.9 *Other Events of Special Interest*

See Core Safety SAP. ³³

7.6.10 *Immune-Mediated Adverse Events*

See Core Safety SAP. ³³

7.6.11 *Laboratory Parameters*

See Core Safety SAP. ³³

7.6.12 *Vital Signs*

See Core Safety SAP. ³³

7.6.13 *Immunogenicity Analysis*

See Core Safety SAP. ³³

7.6.14 *Pregnancy*

[figure not shown]
See Core Safety SAP. ³³

7.6.15 *Adverse Events By Subgroup*

See Core Safety SAP. ³³ Region subgroups are formed by US/Canada/Europe vs Asia vs Asia excluding Japan vs. Japan.

7.7 *Pharmacokinetics*

The nivolumab concentration data obtained in this study may be combined with data from other studies in the clinical development program to develop a population PK model. This model may be used to evaluate the effects of intrinsic and extrinsic covariates on the PK of nivolumab. In addition, exposure-response analyses with selected efficacy and safety endpoints may be conducted. Results of population PK and exposure response-analyses will be reported separately.

7.8.1 *PD-L1 Expression*

The definition of PD-L1 expression and PD-L1 status is described in [Section 4.3.3](#). Analyses of PD-L1 expression are descriptive in nature and intended to examine the distribution of PD-L1 expression and assess potential association between PD-L1 expression and efficacy measures. All the analyses will be based on baseline PD-L1 expression.

7.8.1.1 *Analyses of PD-L1*

Analyses of PD-L1 will include:

- 1) Examine the distribution of PD-L1 expression

- 2) Assess potential association between PD-L1 expression and efficacy measures
- 3) Evaluate the potential predictive relationship of the PD-L1 status and efficacy measures

- 1) Descriptive statistics of PD-L1 expression and PD-L1 status

- Listing of all PD-L1 IHC data, all randomized subjects
- Summary of tumor specimen acquisition and characteristics, all randomized subjects
- Summary statistics of PD-L1 expression by treatment group as randomized and overall, all PD-L1 quantifiable subjects
- Frequency of PD-L1 categorization or status ($\geq 1\%$, $< 1\%$), including ‘missing’, ‘indeterminate’ and ‘not evaluable’, by treatment group as randomized and overall, all randomized subjects

- 2) Evaluation of associations between PD-L1 status and efficacy measures

Analyses will be based on all randomized subjects if not otherwise specified. Each analysis will be performed for the subgroups listed below if not otherwise specified.

- Each PD-L1 status subgroup
- PD-L1 expression missing or indeterminate or not evaluable subgroup

Analyses for OS:

For each of the subgroups:

- OS curves will be estimated using the KM product limit method for each treatment group. Two-sided, 95% confidence intervals for median OS will be computed by Brookmeyer and Crowley method.

Analyses for ORR per BICR RECIST 1.1:

For each of the subgroups:

- Frequency and percentage of BOR will be summarized for each treatment group as randomized.
- ORR will be computed by treatment group as randomized along with exact 95% CIs using the Clopper-Pearson method.
- Odds ratios between the treatments will be provided along with the 95% CI.

For PD-L1 quantifiable subjects, box plots of PD-L1 expression versus response status will be provided by treatment group as randomized.

Receiver Operating Characteristics (ROC) analysis with BOR (CR+PR vs others) will be performed to help assess whether there is a clinically meaningful threshold of PD-L1 expression.

For PD-L1 quantifiable subjects, plots of ROC curve by treatment group as randomized will be provided.

Analyses for PFS per BICR RECIST 1.1:

For each of the subgroups:

- PFS curves will be estimated using the KM product limit method for each treatment group. Two-sided, 95% confidence intervals for median PFS will be computed by Brookmeyer and Crowley method.

3) Evaluation of the potential predictive relationship of PD-L1 status for efficacy measures

Analyses will be based on all PD-L1 quantifiable subjects.

Analyses for OS:

When appropriate, a Cox proportional hazards regression model will be fitted for OS with treatment (treatment groups as randomized), PD-L1 status, and treatment by PD-L1 status interaction. Although the study is not designed to have appropriate power to formally test the interaction of the model, an interaction test at significance level of 0.2 will warrant further exploration and the following statistics will be reported:

- Interaction p-value
- Hazard ratio of treatment vs. control and its associated 95% CI for each of the PD-L1 status subgroup
- Hazard ratio PD-L1 $\geq 1\%$ vs. $< 1\%$ and its associated 95% CI within each treatment group

Analyses for ORR per BICR RECIST 1.1:

When appropriate, a logistic regression model will be fitted for response status (yes=CR or PR, No=others) with treatment (treatment groups as randomized), PD-L1 status and the treatment by PD-L1 status interaction. Although the study is not designed to have appropriate power to formally test the interaction of the model, an interaction test at significance level of 0.2 will warrant further exploration and the following statistics will be reported:

[figure not shown]
- Interaction p-value
- Odds ratio of treatment vs. control and its associated 95% CI will be reported for each of the PD-L1 status subgroup
- Odds ratio of PD-L1 $\geq 1\%$ vs. $< 1\%$ and its associated 95% CI will be reported for each treatment group

Analyses for PFS per BICR RECIST 1.1:

When appropriate, a Cox proportional hazards regression model will be fitted for PFS with treatment, PD-L1 status, and treatment by PD-L1 status interaction. Although the study is not designed to have appropriate power to formally test the interaction of the model, an interaction test

at significance level of 0.2 will warrant further exploration and the following statistics will be reported:

- Interaction p-value
- Hazard ratio of treatment vs. control and its associated 95% CI for each of the PD-L1 status subgroup
- Hazard ratio PD-L1 $\geq 1\%$ vs. < 1% and its associated 95% CI within each treatment group

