5 SAMPLE SIZE AND POWER

The sample size determination of this study is based on OS comparison between subjects randomized to receive nivolumab and sorafenib. With a total of 726 subjects randomized in a 1:1 ratio to receive nivolumab or sorafenib, approximately 91.5% power will be achieved with an overall type I error 0.05. The sample size determination is based on simulation using R v3.2 for OS. Below are details of the sample size determination.

General assumptions:

- There are assumed 39% HCV-infected subjects among all randomized subjects.
- In the sorafenib arm, median OS is 10 months for non-HCV infected and 14 months for HCV infected.
- Exponential distribution is assumed for OS in each randomized arm.

Estimated cumulated enrollment of randomized subjects is summarized in Table 5-1.

Table 5-1: Estimated Cumulative Number of Randomized Patients

Month	1	2	3	4	5	6	7	8	9	10	11	12	13
HCV	6	17	30	45	61	81	105	131	159	188	218	250	282
Non-HCV	9	25	43	67	98	132	170	210	252	297	345	394	444
All	15	42	73	112	159	213	275	341	411	485	563	644	726

[figure not shown]
Sample size determination for OS

Based on simulations under the assumptions stated above, approximately 726 subjects will be randomized and followed until at least 520 OS events are observed in order to provide 91.5% power for a hazard ratio of 0.74 with a two-sided type I error of 0.05. This accounts for a group sequential testing procedure with one interim analysis and one final analysis. The HR of 0.74 corresponds to a 35% increase in the median OS for both non-HCV infected subjects and HCV infected subjects.

The interim analysis will be conducted when 80% OS events are observed. The alpha allocation for the interim and final analyses is based on the Lan-DeMets alpha spending function approach using an O'Brien-Fleming stopping boundary controlling for a two-sided overall type 1 error of 5%. The stopping boundary will depend on the actual number of OS events observed at the time of the interim analysis and the final analysis. However, if the interim analysis is performed exactly when 80% OS events are observed, then 0.024 alpha will be used for the interim analysis and 0.043 alpha will be used for the final analysis.

It is projected that an observed hazard ratio of 0.80 or less would result in a statistically significant improvement of nivolumab at the interim analysis of OS; and an observed hazard ratio of 0.84 or

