7 STATISTICAL ANALYSES

7.1 General Methods

Unless otherwise noted, the titles in the following subsections describe tabulations of discrete variables, by the frequency and proportion of subjects falling into each category, grouped by treatment (with total). Percentages given in these tables will be rounded and, therefore, may not always sum to 100%. Continuous variables will be summarized by treatment group (with total) using the mean, standard deviation, median, minimum and maximum values. If a missing category is not being presented in the data display, only those subjects with non-missing values for the parameter being assessed are included in the percentage calculation.

Time to event distributions (i.e. PFS, OS, DOR and DDC) will be estimated using the KM method. When appropriate, the median along with the corresponding log-log transformed 95% CI will be estimated. Rates at fixed timepoints (e.g., OS at 12 months) will be derived from the KM estimate along with their corresponding log-log transformed 95% confidence intervals.

Unless otherwise specified, the stratification factors for stratified analysis will be the following ones as entered into the IVRS:

- Etiology (HCV vs non-HCV [ie, HBV and HCC with no history of hepatitis virus infection])
- Vascular invasion and/or extrahepatic spread (present vs absent)
- Geography (Asia vs Non-Asia).

The stratified log-rank test will be performed to test the comparison of time to event distributions (OS and PFS) between two treatment arms.

The stratified hazard ratio between two treatment arms along with CI will be obtained by fitting a stratified Cox model with the treatment group variable as unique covariate.

Confidence intervals for binomial proportions will be derived using the Clopper-Pearson method³⁴.

The difference in rates (e.g., ORR) between the two treatment arms along with their two-sided 95% CI will be estimated using the following Cochran-Mantel-Haenszel (CMH) method of weighting³⁵, adjusting for the stratification factors:

$$\hat{\theta} = \frac{\sum w_i \hat{\theta}_i}{\sum w_i} \sim N \left(\theta, \frac{\sum w_i^2 \left[\frac{p_{ix}(1-p_{ix})}{n_{ix}-1} + \frac{p_{iy}(1-p_{iy})}{n_{iy}-1} \right]}{\left(\sum w_i \right)^2} \right)$$

Where $\hat{\theta}_i = p_{ix} - p_{iy}$ is the rate difference of the i th stratum, $w_i = \frac{n_{ix}n_{iy}}{n_{ix} + n_{iy}}$, and n_{ix} and n_{iy} are the number of subjects randomized to treatments x and y, respectively, in the i th stratum.

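### The part-3 PD-L1 models are unadjusted, so the non-randomized PD-L1 ≥1% vs <1% ratio within each arm could partly reflect etiology; an adjusted version and a table of PD-L1 by factor would show whether it does

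*SAP*

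**What the plan says.** SAP 7.8.1.1, part 3, gives three models for PD-L1 quantifiable subjects, each to be fitted when appropriate.

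- **OS:** a "Cox proportional hazards regression model will be fitted for OS with treatment (treatment groups as randomized), PD-L1 status, and treatment by PD-L1 status interaction".
- **ORR:** "a logistic regression model will be fitted for response status (yes=CR or PR, No=others) with treatment (treatment groups as randomized), PD-L1 status", plus the interaction.
- **PFS:** "a Cox proportional hazards regression model will be fitted for PFS with treatment, PD-L1 status, and treatment by PD-L1 status interaction".

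The listed outputs are the interaction p-value, the treatment ratio in each PD-L1 subgroup, and the PD-L1 ≥1% vs <1% ratio. For OS and PFS the last is a hazard ratio "and its associated 95% CI within each treatment group"; for ORR it is an odds ratio by treatment group. The sentence introducing the list mentions an interaction test at the 0.2 level. It can be read as reporting these statistics only when that level is met.

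SAP 7.1 does not add the factors. Its rule is for the hazard ratio between arms, obtained by "fitting a stratified Cox model with the treatment group variable as unique covariate". The SAP names stratification where it wants it (7.5.1 to 7.5.3, 7.10.1.4, 7.10.2.1), and it does not do so here.

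SAP section 5 assumes that etiology is prognostic: "In the sorafenib arm, median OS is 10 months for non-HCV infected and 14 months for HCV infected". On the descriptive side, SAP 7.8.1.1 part 1 plans "Summary statistics of PD-L1 expression by treatment group as randomized and overall, all PD-L1 quantifiable subjects", and its frequency table of PD-L1 status has the same layout. SAP 7.8.1 states the standing of all this: "Analyses of PD-L1 expression are descriptive in nature and intended to examine the distribution of PD-L1 expression".

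**The concern.** Subjects are randomized to treatment and not to PD-L1 status. Within an arm, the PD-L1 ≥1% and <1% groups may differ in other prognostic factors. The plan's own sample-size assumptions name one such factor for OS. If PD-L1 positivity differs by etiology, some of the etiology effect enters the unadjusted PD-L1 ratio. No visible table crosses PD-L1 with etiology, vascular invasion/extrahepatic spread (VI/EHS) or geography, so a reader could not tell whether this had happened.

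The stakes are modest. No decision in this trial rests on these ratios. They do serve the secondary objective on PD-L1 and efficacy (SAP 3.2), and protocol 8.4.2.4 says that an apparent meaningful association would lead to further biomarker work. A reader should be able to tell a modest PD-L1 signal from a difference in etiology mix.

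**Working it through.** **Plan's own figure.** The PD-L1 models have no stated figure. The OS design reproduces closely: 520 events, HR 0.74 and a two-look Lan-DeMets O'Brien-Fleming boundary at 80% give nominal alphas of 0.0244 and 0.0429, critical HRs of 0.80 and 0.84, and 92.5% power (the plan says 0.024, 0.043, 0.80, 0.84 and 91.5%).

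**Inputs from SAP section 5.** 39% HCV; sorafenib medians 14 (HCV) and 10 months (non-HCV); exponential OS; treatment HR 0.74; Table 5-1 accrual; 726 subjects, 363 per arm. The cut-off is month 33 (protocol 8.1), where these inputs give about 282 sorafenib and 244 nivolumab deaths, 526 in all against 520 planned.

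**Assumed, not in the documents.** The share with PD-L1 ≥1% (20%, with 10% and 30% as a range) and every difference in positivity by etiology.

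**Etiology effect.** Non-HCV vs HCV hazard ratio = 14/10 = 1.4; ln 1.4 = 0.336.

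**Shift with no true PD-L1 effect.** Let a and b be the positivity in HCV and non-HCV subjects.

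- Positive share: p = 0.39a + 0.61b.
- HCV share among positives: q₁ = 0.39a/p.
- HCV share among negatives: q₀ = 0.39(1−a)/(1−p).
- Hand approximation: apparent HR ≈ exp[−0.336(q₁ − q₀)].

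Example with a = 26%, b = 16%: p = 0.1014 + 0.0976 = 0.199; q₁ = 0.1014/0.199 = 0.510; q₀ = 0.2886/0.801 = 0.360; HR ≈ exp(−0.336 × 0.149) = 0.951.

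The large-sample limit of the unadjusted Cox estimate, solved numerically with the accrual and cut-off above, agrees with the approximation:

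| Positivity HCV / non-HCV | q₁ | q₀ | Approx. | Cox limit, sorafenib | Cox limit, nivolumab |
|---|---|---|---|---|---|
| equal | 0.390 | 0.390 | 1.000 | 1.000 | 1.000 |
| 26% / 16% | 0.510 | 0.360 | 0.951 | 0.951 | 0.951 |
| 14% / 24% | 0.272 | 0.420 | 1.051 | 1.051 | 1.051 |
| 32% / 12% | 0.630 | 0.331 | 0.904 | 0.905 | 0.905 |
| 8% / 28% | 0.155 | 0.450 | 1.104 | 1.105 | 1.103 |

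Simulation with 1,000,000 subjects per scenario gives 0.95 to 1.05 for 10 points and 0.90 to 1.11 for 20 points. Stratifying by etiology returns 0.99 to 1.01. At 10% positive, a 10-point difference gives 0.91 to 1.10; at 30% positive, 0.96 to 1.04.

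**Sampling error.** The 95% CI factor is exp[1.96/√(d·p(1−p))]. At p = 0.20 this is exp[1.96/√(282 × 0.16)] = 1.34 for sorafenib and exp[1.96/√(244 × 0.16)] = 1.37 for nivolumab. Both exceed every shift above. They use all 363 subjects per arm; restricting to quantifiable subjects would widen them.

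**Coverage against the etiology-adjusted value** (800 simulated trials of 726 per scenario, 20% positive, Monte Carlo error about 0.8 points near 95%). At 10 points: 93–96% unadjusted, 94–96% stratified. At 20 points: 87–93% unadjusted, 94–96% stratified.

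**What does not move.** The shift is nearly equal in both arms. In the simulations the ratio of the two within-arm HRs stays at 0.99 to 1.01, and the treatment HR within PD-L1 subgroups at 0.74 to 0.75 (true 0.74).

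**Not quantified.** The documents give no prognostic figure for etiology on ORR or PFS, and none for VI/EHS or geography on any endpoint.

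**The case against.** The best defence is that nothing planned is wrong. Part 3 is about the predictive question, which rests on the interaction and on the treatment ratios within PD-L1 subgroups. Both are sound. The PD-L1 ratio within arms is a side output, possibly reported only when the interaction meets 0.2. The stated aim is to describe association, and an unadjusted ratio does that. All of this stands.

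Four stronger readings are tempting and are not supported:

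- **The PD-L1 ratios are confounded.** No document links PD-L1 to etiology. Without such a link the shift is zero.
- **The treatment ratios or the interaction are biased.** The treatment ratios within PD-L1 subgroups are randomized comparisons, and the calculation shows almost no movement in either.
- **The later biomarker work could be triggered wrongly.** The analysis described before that sentence in protocol 8.4.2.4 is Kaplan-Meier curves by arm and PD-L1 subgroup. The later work concerns prediction, so the link to the Cox ratio is indirect.
- **The randomization factors are the full set of confounders.** They are not special for a non-randomized contrast. AFP, Child-Pugh, ECOG and BCLC stage are also recorded. The three factors are a natural minimum because the plan already uses them.

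Two further limits apply. Text between SAP 7.8.1.1 and 7.10 is redacted, so an adjusted analysis or a PD-L1-by-factor table there cannot be excluded. SAP section 9 also permits extra exploratory analyses, though it commits to none.

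What remains is that the visible plan lists a non-randomized ratio, assumes a prognostic factor for OS, and offers no way to see whether the two are connected.

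**Conclusion.** The point holds as a conditional, low-priority improvement to a descriptive analysis. The visible part-3 models leave the within-arm PD-L1 ratio unadjusted, and it could partly reflect etiology.

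For OS, with an assumed 20% positive and no true PD-L1 effect, the apparent hazard ratio is about 0.95 to 1.05 for a 10-point difference in positivity by etiology, and 0.90 to 1.11 for a large, 20-point one. A modest apparent PD-L1 effect could therefore be etiology; on the plan's figures, etiology alone could not explain a large one.

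The size rests on the plan's exponential medians and HCV share, and on assumed PD-L1 prevalence and association. Confidence is medium, because that association is unknown.

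**What to change.** Wherever the within-arm PD-L1 ratios are reported:

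1. Keep the three planned models and label these ratios unadjusted.
2. Beside them, report the OS and PFS Cox models stratified by the three IVRS factors, and the ORR logistic model with those factors as covariates.
3. Tabulate PD-L1 status by etiology, VI/EHS and geography.
4. For ORR, note that responders may be sparse. At assumed response rates of 5–15% and 10–30% positive, an arm of 363 has about 2 (363 × 0.10 × 0.05) to 16 (363 × 0.30 × 0.15) responders with PD-L1 ≥1%. Note also that an adjusted odds ratio can differ through non-collapsibility alone. With no PD-L1–etiology association, an adjusted 2.0 appears as 1.91 to 2.00 unadjusted (assumed ORR of 5–30% in PD-L1 <1%, etiology odds ratio 1.4 to 3.0).
5. Label everything descriptive, and post hoc if added after the June 2019 database lock. State whether the ratios are reported regardless of the interaction result.

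Repeats with CRF or BICR values of VI/EHS are optional; SAP 7.10.1.1 reports a 9.3% IVRS–CRF discrepancy for that factor.

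The cost is three extra fits and one table, with no new data. Precision is almost unchanged. Stratifying OS by all eight strata moves the 95% CI factor from about 1.34 to 1.35 (sorafenib) and 1.37 to 1.38 (nivolumab), assuming 70% VI/EHS present and 40% Asia, neither affecting OS. For ORR, the standard error of the PD-L1 log odds ratio moved from 0.467 to 0.470 at an assumed 7% response rate, and from 0.331 to 0.333 at 15%.
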